# Figure 2Triggers to Recheck and Interrupt Drug in Patients With ALT
≤3×ULN at Baseline and No Symptoms

ALT=alanine aminotransferase; ULN=upper limit of normal

# Figure 3Triggers to Interrupt Drug in Patients With ALT ≤3×ULN at
Baseline, and if (+) Symptoms or Abnormal INR or Bilirubin

ALT=alanine aminotransferase; ULN=upper limit of normal

### 17.2.2 Close Monitoring

- 1. Monitor patient twice or 3 times weekly until liver biochemistries (ALT, AST, ALP, total bilirubin), and coagulation profile (INR) resolve, stabilize or return to within Baseline values. Additional tests (eg, conjugated bilirubin) should also be obtained, as appropriate, at the discretion of the Investigator.
- 2. Monitor liver biochemistries and coagulation profile once a week or less according to the Investigator's judgment if the abnormalities stabilize, resolve or return to within Baseline values, or IMP has been discontinued and the patient is asymptomatic.
- 3. Close Monitoring can be stopped based on the Investigator's clinical judgment once the abnormalities stabilize, resolve or return to within Baseline values; or when there is an alternative documented cause to explain the deterioration.
- 4. Obtain a detailed history for symptoms assessment: appearance or worsening of clinical symptoms of hepatitis (such as right upper quadrant discomfort, fever, fatigue, nausea, vomiting, jaundice, rash, or eosinophilia >5%). If a patient is symptomatic in addition to having elevated laboratory parameters, the drug must be discontinued immediately, and a suspected DILI evaluation must be performed.
- 5. Obtain a more detailed history of prior or concomitant diseases.

- 6. Obtain a history for concomitant medications, acetaminophen, dietary supplements, herbal remedies, other over-the-counter medications, recreational drug use, and special diets.
- 7. If possible, quantify the alcohol consumption to assess for alcoholic hepatitis.
- 8. Obtain a history of exposure to environmental chemical agents.
- 9. If INR is also elevated, a trial of intravenous vitamin K administration may be considered, especially in cholestatic patients.

Follow-Up procedures for patient(s) who meet suspected DILI evaluation criteria in A, **B**, or **C** (laboratory analyses are performed at the central laboratory):

Viral hepatitis serology including:

- 1. Hepatitis A IgM antibody.
- 2. Hepatitis B surface antigen and Hepatitis B Core Antibody (IgM).
- 3. Hepatitis C RNA.
- 4. Hepatitis E IgM antibody.
- 5. Cytomegalovirus IgM antibody.
- 6. Epstein-Barr viral capsid antigen IgM antibody (or if unavailable, obtain heterophile antibody or monospot testing); however, IgM antibodies must be sent out as soon as possible.

Follow-up signs and symptoms consistent with potential immune mediated injury and, if relevant, monitor until the abnormalities resolve and to EoT Visit.

- 1. Fever, malaise, pruritus, etc.
- 2. Rash.
- 3. Edema.
- 4. Lymphadenopathy.
- 5. Hematological changes (leukopenia, anemia, thromobocytopenia, etc.), urinalysis, ECG etc.
- 6. Other organ involvement, in addition to liver (kidney, heart, lungs, etc.).

Other laboratory tests and assessments including:

- 1. Serum Creatine phosphokinase and lactate dehydrogenase.
- 2. Fractionate bilirubin, if total bilirubin >2×ULN.

- 3. A liver biopsy at the discretion of the Investigator.
- 4. Assess for peripheral eosinophilia. Investigators are also encouraged to obtain a skin biopsy in subjects who have liver enzyme elevation together with eosinophilia.
- 5. Assess for hypoxic/ischemic hepatopathy, and biliary tract disease.

As long as Criteria A, B or C are met WITHOUT identification and documentation of an alternative cause, these abnormal liver tests will be considered suspected DILI and be reported to the Sponsor as AESI and go for adjudication. Once an alternative cause has been identified and documented, for the laboratory abnormalities qualifying Criteria A, B, or C of Appendix II, the alternative clinical event is to be reported as an AE/SAE.

In addition, undertake the following for patients who meet the stopping criteria for both ALT and total bilirubin OR experiences clinical symptoms of hepatitis:

- 1. Antinuclear antibody, antismooth muscle antibody, Type 1 anti-liver kidney microsomal antibodies and quantitative total immunoglobulin G (IgG or gamma globulins). Analyses are performed at the central laboratory.
- 2. If required, evaluation of competing undiagnosed liver disease (hemochromatosis, Wilson's disease, alpha-1 anti-trypsin deficiency).
- 3. Serum acetaminophen levels OR serum acetaminophen adducts by high performance liquid chromatography assay (quantifies potential acetaminophen contribution to liver injury in patients with definite or likely acetaminophen use in the preceding week).
- 4. Liver imaging (ultrasound, magnetic resonance, or computerized tomography) to evaluate liver disease at the discretion of the Investigator.

#### 17.3 APPENDIX III – MELD Score

The MELD score will be calculated based on the results from the liver biochemistry (total bilirubin), biochemistry (creatinine, and sodium if MELD score >11), and hematology (INR) blood samples, according to the following formulas:

- a. **MELD** =  $3.78 \times \ln[\text{serum bilirubin (mg/dL)}] + 11.2 \times \ln[\text{INR}] + 9.57 \times \ln[\text{serum creatinine (mg/dL)}] + 6.43$
- b. When MELD>11: MELD-Na = MELD + 1.32×(137 Na (mmol/L) (0.033×MELD×(137 Na (mmol/L))))

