### 4.2 Exclusion Criteria

A patient who meets any of the following exclusion criteria will not be eligible for inclusion in the study:

- 1. A positive pregnancy test or breastfeeding for female patients.
- 2. Any historical or current hepatic decompensation event defined as variceal/portal hypertension bleed and/or hepatic encephalopathy, spontaneous bacterial peritonitis, ascites requiring treatment, or liver transplantation list inclusion.
- History of liver transplantation, current placement on a liver transplant list or current MELD score of ≥12 unless the patient is on anticoagulant therapy, or a Child-Pugh Score of ≥6.
- 4. Cirrhosis with complications, including history or presence of hepatocellular carcinoma.
- 5. Total bilirubin >2×ULN. In case of total bilirubin elevation >ULN the Screening serum albumin must be within the reference range.

One repeat blood sampling (with analysis by the central laboratory) can be performed at the discretion of the Investigator at Screening Visit 2 for patients who meet this exclusion criterion at Screening Visit 1. If this exclusion criterion is not met at Screening Visit 2, the patient may be eligible for the study.

6. Plasma ALT >3×ULN and/or AST >3×ULN.

One repeat blood sampling (with analysis by the central laboratory) can be performed at the discretion of the Investigator at Screening Visit 2 for patients who meet this exclusion criterion at Screening Visit 1. If this exclusion criterion is not met at Screening Visit 2, the patient may be eligible for the study. 7. INR >1.2 unless patient is on anticoagulant therapy.

One repeat blood sampling (with analysis by the central laboratory) can be performed at the discretion of the Investigator at Screening Visit 2 for patients who meet this exclusion criterion at Screening Visit 1. If this exclusion criterion is not met at Screening Visit 2, the patient may be eligible for the study.

- 8. Estimated glomerular filtration rate (eGFR) <30 mL/min/1.73 m^2, as calculated by the central laboratory using the chronic kidney disease epidemiology collaboration (CKD-EPI) equation.
- 9. TSH >ULN at Screening.

One repeat blood sampling (with analysis by the central laboratory) can be performed at the discretion of the Investigator at Screening Visit 2 for patients who meet this exclusion criterion at Screening Visit 1. If this exclusion criterion is not met at Screening Visit 2, the patient may be eligible for the study.

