#### 5.4 Adverse Clinical Outcomes

The following adverse clinical outcomes will be captured during the study:

- All-cause mortality
- Patients requiring a liver transplant (transplant list inclusion)
- MELD score of ≥15 (confirmed at repeat testing at least 14 days apart), as calculated by the central laboratory, according to the formulas in Appendix III

The MELD score will be calculated based on the results from the liver biochemistry (total bilirubin), biochemistry (creatinine, and sodium if MELD score >11), and hematology (INR) blood samples, collected as described in Section 5.3.2.

- Variceal bleed
- Portal hypertension bleed
- Hepatic encephalopathy (West Haven criteria), see Appendix IV
- Spontaneous bacterial peritonitis
- Uncontrolled ascites requiring treatment

In the event of any of these outcomes, IMP will be permanently discontinued, as noted in Section 4.4.1, and the patient may continue study visits.

Investigators will record the AEs in the Adverse Event page of the eCRF and will indicate on the Adverse Event page if it meets the criteria for an SAE. If the event meets

the criteria of an SAE, it will be reported using the paper safety report form within 24 hours of becoming aware of the event.

The adverse clinical outcomes will be adjudicated by the Adjudication Committee (see Section 9.4.1).

Investigators will indicate on the eCRF Adverse Event page if the event meets the criteria for adjudication. If the event meets the criteria for adjudication, the Investigator will then complete the Adjudication Event eCRF.

Please refer to the Investigator adjudication manual for further information.

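### The sodium term in Appendix III has no upper limit, so for sodium above 137 mmol/L the MELD score drops as severity passes 11, and the SAP describes MELD without sodium

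*Protocol*

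**What the plan says.** Appendix III (protocol 17.3) gives two formulas. Formula (a) is 3.78 times the log of bilirubin, plus 11.2 times the log of INR, plus 9.57 times the log of creatinine, plus 6.43. Formula (b) adds sodium: "When MELD>11: MELD-Na = MELD + 1.32×(137 Na (mmol/L", followed by a 0.033 × MELD × (137, Na) term. The inputs are described as "biochemistry (creatinine, and sodium if MELD score >11), and hematology (INR) blood samples, according to the following formulas". Neither formula limits any input, and nothing elsewhere in the protocol or SAP does so.

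The score is used in several places:

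- Exclusion criterion 3 (protocol 4.2): "current MELD score of ≥12 unless the patient is on anticoagulant therapy, or a Child-Pugh Score of ≥6".
- The MELD ≥15 adverse clinical outcome (protocol 5.4), confirmed on repeat testing, "as calculated by the central laboratory, according to the formulas in Appendix III". It is an exploratory endpoint (2.3), is adjudicated (9.4.1) and is a reason to discontinue IMP (4.4.1, item 10).
- Baseline MELD in SAP 12.2, the MELD ≥15 safety summary in SAP 12.6.2 and the listing flags in SAP 12.6.3.

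SAP 12.6.3 describes the laboratory's calculation from bilirubin, creatinine and INR only. Protocol 5.2.4.3, 5.4 and Appendix III all add sodium when MELD exceeds 11.

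**The concern.** A severity score should not fall when its own severity input rises. Formula (b) switches on just above 11 and, for sodium above 137 mmol/L, subtracts points at that moment. Both decision points, 12 and 15, lie above the switch. Patients whose raw score exceeds 12 or 15 can therefore be classed below it because their sodium is slightly above 137. The eligibility decision, the exploratory outcome and the trigger for stopping IMP all depend on this. Because the SAP describes a score without sodium, the analysis outputs may also disagree with the classification used during the trial.

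**Working it through.** The documents give no worked MELD value, so there is no figure of the plan to reproduce. The check evaluates the Appendix III formulas directly.

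**Inputs.** The coefficients are those of Appendix III. Write M for the result of formula (a), called raw MELD here, and d = 137 − Na. The minus signs were lost when the PDF was read, and that loss is not part of the point. Two bracket readings are carried throughout:

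- Reading 1: M + 1.32d − 0.033Md.
- Reading 2 (printed brackets taken literally): M + 1.32(d − 0.033Md).

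**Direction.** Reading 1 adds d(1.32 − 0.033M). This is negative for Na above 137 whenever M is below 1.32/0.033 = 40. Reading 2 adds 1.32d(1 − 0.033M), negative for M below 1/0.033 = 30.3. Sodium of 137 is neutral, and 135 or 136 raises the score.

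**Drop at the switch, Na 140 (d = −3).** M = 11.0 stays 11.0. For M = 11.1:

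- Reading 1: 11.1 − 3.96 + 0.099 × 11.1 = 8.2.
- Reading 2: 11.1 + 1.32(−3 + 0.099 × 11.1) = 8.6.

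The score returns to 11.0 only when M reaches (11 + 3.96)/1.099 = 13.6.

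**Raw MELD needed to score T.** Reading 1: (T − 1.32d)/(1 − 0.033d). Reading 2: (T − 1.32d)/(1 − 1.32 × 0.033d).

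| Na (mmol/L) | To score 12, reading 1 (2) | To score 15, reading 1 (2) |
|---|---|---|
| 137 | 12.00 (12.00) | 15.00 (15.00) |
| 138 | 12.89 (12.76) | 15.80 (15.64) |
| 140 | 14.52 (14.12) | 17.25 (16.77) |
| 142 | 15.97 (15.27) | 18.54 (17.74) |
| 145 | 17.85 (16.73) | 20.22 (18.95) |

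**Entry example.** Bilirubin 1.9 mg/dL, INR 1.2, creatinine 1.3 mg/dL, Na 140, not anticoagulated. This assumes that 1.9 mg/dL is within 2×ULN, albumin is in range and eGFR is at least 30.

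- M = 2.43 + 2.04 + 2.51 + 6.43 = 13.4, which would be excluded.
- Score = 13.41 − 3.96 + 0.099 × 13.41 = 10.8 (reading 2: 11.2), which passes.

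Every logged input exceeds 1, so no assumed floor is involved.

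**Who is affected at entry.** All five Child-Pugh components score at least 1, so excluding a total of 6 or more forces bilirubin below 2 mg/dL (Appendix V). INR is held to 1.2 by "INR >1.2 unless patient is on anticoagulant therapy". With creatinine at 1.0, M is therefore below 6.43 + 3.78 ln 2 + 11.2 ln 1.2 = 11.09. To reach 12, creatinine must exceed exp((12 − 11.09)/9.57) = 1.10 mg/dL at the extreme corner. On a grid in steps of 0.05, the first affected value is 1.15. The renal criterion, "Estimated glomerular filtration rate (eGFR) <30 mL/min/1.73 m", leaves room for such values.

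**Outcome example.** Bilirubin 3.5, INR 1.5, creatinine 1.0, Na 140.

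- M = 4.74 + 4.54 + 0 + 6.43 = 15.7, which meets 15.
- Score = 13.3 (reading 2: 13.8), which misses it. By the SAP 12.6.3 description, without sodium, the same patient scores 15.7.

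**Logged inputs below 1.** 9.57 ln(0.7) = −3.4. The same patient with creatinine 0.7 and Na 137 scores 12.3. This is under-calling only if the intended algorithm floors inputs at 1.0, which the documents do not say.

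**The case against.** The best defence is that the central laboratory supplies the score (protocol 5.2.4.3) and its manual is not among the documents; it may already limit the inputs. That is possible. But protocol 5.4 ties the calculation to Appendix III, so the formulas there are the specified ones. If the laboratory applies limits, the protocol should state them.

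A second defence is that little rests on the score. MELD ≥15 is exploratory, bilirubin above 2×ULN or INR above 1.5 triggers its own retest under Appendix II, and clinical decompensation events are separate outcomes. This stands and limits the consequences, but it does not make the formula right.

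A reader might also infer more than the documents support:

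- *That low creatinine lets sicker patients in, especially given the 9:1 female ratio.* The INR and Child-Pugh limits hold a creatinine-floored score to 11.09, so low creatinine practically cannot change entry. The one sliver is a floored score between 11.0 and 11.09 with low sodium. Anticoagulated patients are exempt in any case: "current MELD score of ≥12 unless the patient is on anticoagulant therapy".
- *That any normal sodium lowers the score.* Only values above 137 do.
- *That logs without a floor are an error in themselves.* A log below 1 is negative by nature. Calling it wrong needs an outside convention.
- *That the cholestasis responder analysis in SAP 12.5.4.1 is distorted.* Each criterion already requires bilirubin at or below 1×ULN or less. With creatinine 1.0 and an assumed ULN of 1.0 to 1.3 mg/dL, MELD 15 would need INR of about 2.15 to 2.0, from exp((15 − 6.43 − 3.78 ln bilirubin)/11.2). The effect is close to nil.

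**Conclusion.** Formula (b) is wrong as written for sodium above 137 mmol/L: the score drops as raw MELD passes 11. At sodium 140 it asks for 2.5 raw points more to score 12 (14.5 − 12) and 2.3 more to score 15 (17.3 − 15), or 2.1 and 1.8 with the literal brackets. The entry effect is confined to patients not on anticoagulants with creatinine of about 1.15 mg/dL or more. The MELD ≥15 outcome can be under-called through sodium and, if floors of 1.0 were intended, through low logged inputs as well. Separately, the protocol includes sodium and SAP 12.6.3 does not, and this needs reconciling whichever formula is right.

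The conclusion assumes the missing signs are minus signs and that the laboratory followed Appendix III. How many patients are affected cannot be judged from the documents. The primary ALP analysis does not use MELD and is untouched.

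**What to change.** 1. Confirm with the central laboratory which algorithm it actually ran, including any input limits.
2. Correct Appendix III so that the sodium term cannot lower the score as MELD passes 11, and state that algorithm's input limits and bracket placement.
3. Reconcile SAP 12.6.3 with the corrected appendix, so that one definition of MELD serves the protocol and all outputs.
4. Recompute MELD from stored central laboratory values for SAP 12.2, 12.6.2 and 12.6.3, and list every patient whose classification at 12 or 15 changes.

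The thresholds themselves and the IMP discontinuation rule are for the sponsor to reconcile; nothing here proposes changing them.

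The cost is a wording change in one appendix and one SAP section, plus reprogramming on data already held. A few patients may be reclassified, either as MELD ≥15 or as having been at 12 or above at entry.

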#### 17.4 APPENDIX IV – West Haven Criteria and Clinical Description

WHC including MHE	Description	Suggested Operative Criteria	Comment
Unimpaired	No encephalopathy at all, no history of HE	Tested and proved to be normal	
Minimal	Psychometric or neuropsychological alterations of tests exploring psychomotor speed/executive functions or neurophysiological alterations without clinical evidence of mental change	Abnormal results of established psychometric or neuropsychological tests without clinical manifestations	No universal criteria for diagnosis Local standards and expertise required
Grade I	
 
Trivial lack of awareness
 
Euphoria or anxiety
 
Shortened attention span
 
Impairment of addition or subtraction
 
Altered sleep rhythm
 
	Despite oriented in time and space (see below), the patient appears to have some cognitive/behavioral decay with respect to his or her standard on clinical examination or to the caregivers	Clinical findings usually not reproducible
Grade II	
 
Lethargy or apathy
 
Disorientation for time
 
Obvious personality change
 
Inappropriate behavior
 
Dyspraxia
 
Asterixis
 
	Disoriented for time (at least 3 of the followings are wrong: day of the month, day of the week, month, season, or year) $\pm$ the other mentioned symptoms	Clinical findings variable, but reproducible to some extent
Grade III	
 
Somnolence to semistupor
 
Responsive to stimuli
 
Confused
 
Gross disorientation
 
Bizarre behavior
 
	Disoriented also for space (at least 3 of the following wrongly reported: country, state [or region], city, or place) $\pm$ the other mentioned symptoms	Clinical findings reproducible to some extent
Grade IV	Coma	Does not respond even to painful stimuli	Comatose state usually reproducible

HE=hepatic encephalopathy; MHE=minimal hepatic encephalopathy; WHC=West Haven Criteria All conditions are required to be related to liver insufficiency and/or portosystemic shunting. Source: Vilstrup et al 2014

#### 17.5 APPENDIX V – Child-Pugh Classification of Severity of Cirrhosis

Modified Child-Pugh classification of the severity of liver disease according to the degree of ascites, the serum concentrations of bilirubin and albumin, the prothrombin time, and the degree of encephalopathy is assessed as described in the table below.

A total Child-Turcotte-Pugh score of 5 to 6 is considered Child-Pugh class A (well-compensated disease), 7 to 9 is class B (significant functional compromise), and 10 to 15 is class C (decompensated disease). These classes correlate with one- and two-year patient survival: class A: 100% and 85%; class B: 80% and 60%; and class C: 45% and 35%.

Description	Points assigned			
Parameter	1	2	3	
Ascites	Absent	Slight	Moderate	
Bilirubin	<2 mg/dL (<34.2 µmol/L)	2 to 3 mg/dL (34.2 to 51.3 μmol/L)	>3 mg/dL (>51.3 µmol/L)	
Albumin	>3.5 g/dL (35 g/L)	2.8 to 3.5 g/dL (28 to 35 g/L)	<2.8 g/dL (<28 g/L)	
Prothrombin time (seconds over control) or	<4	4 to 6	>6	
INR	<1.7	1.7 to 2.3	>2.3	
Encephalopathy	None	Grade 1 to 2	Grade 3 to 4	

INR=international normalized ratio.

Source: https://www.uptodate.com/contents/image?imageKey=GAST%2F78401

2.0 Change History

Version/Date	Change Log
0.1/17 August 2021	Created as new
0.2/20 December 2021	Updated for Protocol Version 2.0 and Sponsor Comments on V0.1
0.3/10 June 2022	Updated to align with TFL shells
0.4/3 October 2022	Updated per Sponsor comments on V0.3 and FDA feedback on V0.2
0.5/15 February 2023	Updated per Sponsor comments on V0.4 and Protocol Amendment version 4.0
1.0/17 February 2023	Updated per Sponsor comments on V0.5 and moving to stable version.
1.1/27 October 2023	Updated per Protocol Amendment version 5.0
1.2/01 November 2023	Updated per Sponsor comments on V1.1
2.0/02 November 2023	Moving to stable version V2.0 from V1.2
3.0/06 June 2024	Updated per Sponsor comments on dry-run #1
3.0/27 June 2024	Updated per Sponsor comments on dry-run #2

Sponsor: Calliditas Therapeutics Suisse SA Protocol No: GSN000350

4.0 Purpose

The Statistical Analysis Plan (SAP) describes the statistical methods to be used during the reporting and analyses of data collected under Calliditas Therapeutics Suisse SA Protocol GSN000350 Amendment version 5.0.

5.0 Scope

This Statistical Analysis Plan outlines the following:

- Study Objectives
- Study Design
- Study Estimands
- Analysis Sets
- Conventions and Definitions
- Applicable Study Definitions
- Statistical Methods

6.0 Introduction

This SAP should be read in conjunction with the study protocol and case report forms (CRF). This version of the plan has been developed by ICON using the protocol version 5.0 dated 27-Sep-2023 and CRF version 6.0 dated 03-Aug-2023. Any further changes to the protocol or CRF that have an impact on the design, or the planned statistical analysis will require updates to the SAP.

The TRANSFORM study was initiated as a randomized, placebo controlled, double-blind, adaptive Phase 2b/3 study with a 52-week treatment period and a 52-week open-label extension period. Enrolment into the study has been significantly slower than predicted and the feasibility of conducting the study within an acceptable timeframe has proven challenging. This is considered related to new and more frequently used treatment options, such as obeticholic acid (OCA) and off-label use of fibrates. One consequence of this is that fewer subjects are meeting the inclusion criteria for alkaline phosphatase (ALP) ≥ 1.67*ULN.

Considering the challenges, under protocol version 5.0, the study has been revised to a randomized, placebo-controlled, double-blind, **Phase 2b** study of setanaxib in **60-70** subjects with PBC and elevated liver stiffness, to assess the safety and efficacy of the 1200 mg and 1600 mg doses of setanaxib versus placebo over a **24-week treatment period**. The primary endpoint has been amended to evaluate change in ALP (%) on a continuous scale at 24 weeks, rather than the originally planned (binary) composite endpoint of change in ALP and total bilirubin at 52 weeks which requires a significantly larger sample size. The secondary endpoints of change in fatigue and liver stiffness are retained, as is the composite endpoint of changes in markers of cholestasis. The rationale for a 52-week Extension Phase Treatment Period and for an interim analysis is no longer applicable; therefore, the Extension Period, the 12-week Follow-up Period and interim analysis have been removed. A detailed rationale for changes to the study design is described in Protocol Amendment version 5.0 Section 1.2. The results from this Phase 2b study will inform the future development of setanaxib in PBC.

This SAP describes the statistical methods that will be used for the analysis of this Phase 2b study and for summarizing data captured under previous versions of the protocol (v1.0 to 4.0). The first version of the SAP was developed and submitted to the FDA in December 2021, prior to enrollment of the first subject. Since this time, the Investigators, Subjects in the study, Sponsor and ICON have remained blind to randomized treatment assignment. Furthermore, team members operating in a blinded capacity have not been granted access to data concerning ALP and bilirubin values over the course of the study. Consequently, any modifications to the ongoing study have not been influenced in any manner by emerging data or results derived from the study.

The final version of the SAP will be finalized before the database is locked; subsequent to this stage, team members working in a blinded capacity will undergo an unblinding process to reveal the actual randomized assignments.

Sponsor: Calliditas Therapeutics Suisse SA

Protocol No: GSN000350

